Eight skin lesions in 7 of 337 vemurafenib-treated patients were reported as new primary malignant melanomas in Study NO25026. No cases were reported in 338 patients treated with DTIC. Cases were managed with excision and without sequelae, and patients continued treatment without dose adjustment. Surveillance measures to monitor for the occurrence of new primary melanomas as well as cuSCC are outlined in Section 4.5.1.5, Section 4.5.2.2, and Section 5.1.2.3. Details for Study NO25026 are summarized in the Vemurafenib IB.

The effects of vemurafenib on the QT interval were investigated as part of the Phase II Study NP22657. This was not a “thorough” QT study as defined by health authorities because vemurafenib cannot be administered to healthy volunteers and it was not feasible to administer a positive or negative control to patients with metastatic melanoma. However, the centrally read ECG data obtained in triplicate at serial, time-matched points before and after dosing met the regulatory expectations for robust assessment of oncology therapeutics on the QT interval. The maximum absolute corrected QT (QTc) values at any point after dosing were as follows: >450 milliseconds (ms), 49 patients (37.1%); >480 ms, 6 patients (4.5%); >500 ms (Grade 3), 2 patients (1.5%). One patient (0.8%) had a maximal QTc increment >60 ms (Grade 2) compared with baseline. The upper boundary of the one-sided 95% CI for mean QTc prolongation reached a maximum of 17.7 ms on Day 105 of study treatment, on the basis of measurements in 90 patients. Mean QTc interval prolongation closely tracked with the mean vemurafenib steady-state concentration over time. None of the QT prolongation events were serious or led to premature withdrawal from treatment or dose modification/interruption; none were clearly associated with prolongation of cardiac repolarization, arrhythmia, or any other cardiac function disorder. Additional information on the relationship between vemurafenib exposure and QT interval prolongation may be found in the Vemurafenib IB.

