5.1.2.3.3 Cutaneous Squamous Cell Carcinoma (including Keratoacanthoma) and New Primary Melanoma

For all patients, a complete evaluation of the skin by a designated dermatologist or his or her designee who is experienced in the diagnosis and management of cuSCC/KA will be conducted at baseline (up to 90 days prior to randomization), during study drug treatment period, and post-treatment follow-up according to Section 4.5.2 and Appendix 1. An unscheduled dermatology examination may be performed for investigation of any new skin lesions that are suspected of being cuSCC (including those classified as KA) or new primary melanomas. If a patient develops cuSCC/KA either during or after the study drug administration period, this information must be collected and reported as a non-serious adverse event of special interest to the Sponsor, whether it is deemed related or unrelated to study drug. If a patient develops a new primary melanoma either during or after the study drug administration period, this information must be collected and reported to the Sponsor, whether it is deemed related or unrelated to study drug. The following bullet points detail the required monitoring/management of skin-associated vemurafenib risks:

- A dermatologist or his or her designee who is experienced in the diagnosis and management of cutaneous neoplasms will perform skin evaluations to monitor for cuSCC/KA, new primary melanoma, BCC, and actinic keratosis.
- A complete history of prior dermatologic interventions and medications, cuSCC risk factors (i.e., Fitzpatrick skin type, radiotherapy, sun exposure, immunosuppression, prior SCC, use of tanning beds, and precursor lesions), and prior HPV vaccination must be collected. Refer to Appendix 7 for a list of Fitzpatrick skin phototypes.
- Any suspicious lesions identified at baseline and while on study drug and 26 ± 2 weeks after last dose of study drug must be biopsied and excised and sent for pathological examination.
- Available specimen block/sections should be sent to a Roche-designated central pathology laboratory for confirmation of diagnosis and further molecular characterization.

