5.1.2.3.5 New Primary Cancers

All new primary malignancies will be reported *until end of study* (see Section 3.2), whether or not a patient has exhibited recurrence of melanoma in the study.

Visual and digital evaluation of the anus and anal canal will be performed according to Section 4.5.2 and Appendix 1. For female patients, a pelvic examination, including visual inspection of the uterine cervix and Pap smear, will occur according to Section 4.5.2 and Appendix 1.

For all patients, a thorough evaluation of the head and neck will be performed as part of the physical examination by the site investigator according to Section 4.5.2 and Appendix 1. Evaluation will consist of at least a visual inspection of the oral mucosa and palpation of the tonsils, base of tongue, and lymph nodes.

If, at any time, head and neck cancer is suspected (e.g., on the basis of signs or symptoms), the patient will be referred to a head and neck surgeon/otorhinolaryngologist or designee who is experienced in the diagnosis and management of SCC of the head

and neck. The head and neck surgeon/otorhinolaryngologist or designee will perform an assessment including at least a visual inspection of the oral mucosa, palpation of the tonsils, base of tongue, and lymph nodes and flexible fiberoptic laryngoscopy in order to evaluate at least the sinonasal cavity, the nasopharynx, the base of tongue, the larynx, and the hypopharynx. For patients who have been referred to a head and neck surgeon/otorhinolaryngologist or designee who is experienced in the diagnosis and management of SCC of the head and neck, this assessment will occur at screening and every 26 ± 2 weeks during the study drug administration period. Patients who complete the treatment period or discontinue study drug early will have this assessment at 26 ± 2 weeks after the last dose of study drug (except in the case of withdrawal of consent or loss to follow-up).

If a patient develops a new primary malignancy (other than cuSCC/KA or melanoma) either during or after study treatment, this information must be collected and reported as a serious adverse event to the Sponsor, whether it is deemed related or unrelated to study drug. If the patient is still receiving study drug, the investigator should contact the Medical Monitor to discuss study drug administration. For cuSCC/KA or new primary melanoma, refer to Section 5.1.2.3.3.

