5.2.2 Serious Adverse Events (Immediately Reportable to Roche)

A serious adverse event is any adverse event that meets any of the following criteria:

- Fatal (i.e., the adverse event actually causes or leads to death)
- Life threatening (i.e., the adverse event, in the view of the investigator, places the patient at immediate risk of death)

This does not include any adverse event that, had it occurred in a more severe form or was allowed to continue, might have caused death.

- Requires or prolongs inpatient hospitalization (see Section 5.3.5.9)
- Results in persistent or significant disability/incapacity (i.e., the adverse event results in substantial disruption of the patient’s ability to conduct normal life functions)
- Congenital anomaly/birth defect in a neonate/infant born to a mother exposed to study drug
- Significant medical event in the investigator's judgment (e.g., may jeopardize the patient or may require medical/surgical intervention to prevent one of the outcomes listed above)

A new primary malignancy (other than cuSCC/KA) or progression or recurrence of a prior malignancy (other than the disease under study) will be categorized as a serious adverse event.

Recurrence of melanoma is not reported as an adverse event if it is clearly consistent with the suspected recurrence of the disease under study. Clinical signs or symptoms of recurrence may be reported as adverse events only if the symptom cannot be determined as exclusively due to the recurrence of the underlying malignancy or does not fit the expected pattern of recurrence for the disease under study. If there is any uncertainty about an adverse event being due only to the extent of the disease under study, it should be reported as an adverse event or a serious adverse event.

The terms “severe” and “serious” are not synonymous. Severity refers to the intensity of an adverse event (rated as mild, moderate, or severe, or according to NCI CTCAE; see Section 5.3.3); the event itself may be of relatively minor medical significance (such as severe headache without any further findings).

Severity and seriousness need to be independently assessed for each adverse event recorded on the eCRF.

Serious adverse events are required to be reported by the investigator to the Sponsor within 24 hours after learning of the event (see Section 5.4.2 for reporting instructions).

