5.6 POST-STUDY ADVERSE EVENTS

At the study treatment completion/early termination visit, the investigator should instruct each patient to report to the investigator any subsequent adverse events that the patient's personal physician believes could be related to prior study drug treatment or study procedures.

The investigator should notify the Sponsor of any death, serious adverse event (including new primary malignancies), or other adverse event of concern occurring at any time after a patient has discontinued study participation if the event is believed to be related to prior study drug treatment or study procedures. The Sponsor should also be notified if the investigator becomes aware of the development of cancer or a congenital anomaly/birth defect in a subsequently conceived offspring of a patient that participated in this study.

The investigator should report these events to Roche Safety Risk Management on the Adverse Event eCRF. If the Adverse Event eCRF is no longer available, the investigator should report the event directly to Roche Safety Risk Management via telephone (see Protocol Administrative and Contact Information & List of Investigators).

During survival follow-up, deaths attributed to recurrence of melanoma should be recorded on the Study Completion/Discontinuation eCRF.

5.7 EXPEDITED REPORTING TO HEALTH AUTHORITIES, INVESTIGATORS, INSTITUTIONAL REVIEW BOARDS, AND ETHICS COMMITTEES

To determine reporting requirements for single adverse event cases, the Sponsor will assess the expectedness of these events using the following reference documents:

- Vemurafenib IB
- Local prescribing information for vemurafenib
- Vemurafenib Core Data Sheet

The Sponsor will compare the severity of each event and the cumulative event frequency reported for the study with the severity and frequency reported in the applicable reference document.

Reporting requirements will also be based on the investigator's assessment of causality and seriousness, with allowance for upgrading by the Sponsor as needed.

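### Protocol 5.2.2 makes new primary melanoma an SAE, but 5.1.2.3.5 leaves it out of its SAE instruction and no section gives it another category, so SAE counts by arm may be inconsistent

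*Protocol*

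**What the plan says.** Five places in the protocol bear on how a new primary melanoma is reported.

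- **5.2.2 (definition of an SAE)** puts into the serious category "A new primary malignancy (other than cuSCC/KA) or progression or recurrence of a prior malignancy (other than the disease under study". The only new primary exempted is cuSCC/KA.
- **5.1.2.3.5 (new primary cancers)** gives its SAE instruction with a wider exemption: "If a patient develops a new primary malignancy (other than cuSCC/KA or melanoma) either during or after study treatment". For the exempted tumours it says: "For cuSCC/KA or new primary melanoma, refer to Section 5.1.2.3.3".
- **5.1.2.3.3** first classifies cuSCC/KA explicitly: "this information must be collected and reported as a non-serious adverse event of special interest to the Sponsor". For melanoma it then asks only that the case be passed on: "new primary melanoma either during or after the study drug administration period, this information must be collected and reported to the Sponsor". It names no category.
- **5.2.3** lists the adverse events of special interest. cuSCC (including KA) is on the list; new primary melanoma is not.
- **5.6** covers events after study participation that are believed related to treatment or procedures. It speaks of a "serious adverse event (including new primary malignancies" and makes no exception for melanoma.

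Protocol 5.3 refers the investigator to 5.2.2 for the assessment of seriousness.

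SAE incidence is a stated safety outcome (Protocol 3.4.2, SAP 2.1.5). It is tabulated by arm for each cohort and pooled (Protocol 6.5, SAP 4.7.2), and SAEs were part of the quarterly safety-board tables (Protocol 5.1.2.2).

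**The concern.** A site working from the definition in 5.2.2 files a new primary melanoma as an SAE. A site working from the section on new primary cancers finds melanoma removed from the SAE instruction, follows the cross-reference, and arrives at a sentence with no category. The same event can then be serious at one site and not at another.

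Two things depend on this. One is the SAE count by arm: SAP 4.7.2 gives new primary melanoma no line of its own, so a reader of the SAE table could not tell whether it is included. The other is timing. The 24-hour duty in Protocol 5.4 attaches to SAEs, events of special interest and pregnancies. An event that is neither serious nor of special interest has no clear 24-hour duty.

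The event is also one where a difference between arms is plausible. Protocol 1.2.5 reports: "Eight skin lesions in 7 of 337 vemurafenib-treated patients were reported as new primary malignant melanomas in Study NO25026". It reports none among 338 patients on dacarbazine.

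**Working it through.** **1. The texts side by side**

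| Protocol section | cuSCC/KA | New primary melanoma | Other new primary malignancy |
|---|---|---|---|
| 5.2.2 | exempt from the SAE category | SAE | SAE |
| 5.1.2.3.5 | exempt; see 5.1.2.3.3 | exempt; see 5.1.2.3.3 | SAE |
| 5.1.2.3.3 | non-serious event of special interest | report to Sponsor, no category | not addressed |
| 5.2.3 | listed | not listed | not listed |
| 5.6 | no exception stated | no exception stated | counted among SAEs |

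Only the melanoma column has no consistent answer. For cuSCC/KA, sections 5.2.2, 5.1.2.3.5, 5.1.2.3.3 and 5.2.3 agree.

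**2. Does 5.2.2 exempt melanoma in some other way?** No. Its bracket about the disease under study qualifies progression or recurrence of a prior malignancy; new primary malignancy has its own bracket, limited to cuSCC/KA. The later paragraph that keeps melanoma out of adverse event reporting concerns recurrence only. The protocol treats recurrence and new primary melanoma as separate events, for instance in the DFS definition (3.4.1.1).

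**3. How many patients?** The plan gives no figure to reproduce. An illustrative size follows from the protocol's own data.

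- Inputs: 7/337 on vemurafenib and 0/338 on dacarbazine (Protocol 1.2.5); about 475 patients randomized 1:1 (Protocol 3.1), so 475/2 = 237.5, taken as 237 per arm.
- Vemurafenib rate: 7/337 = 2.1%. The exact (Clopper-Pearson) 95% limits are the 2.5% quantile of Beta(7, 331) = 0.8% and the 97.5% quantile of Beta(8, 330) = 4.2%.
- Comparator: 0/338. The upper limit is 1 − 0.025^(1/338) = 1.1%.
- Two-sided Fisher exact test of 7/337 vs 0/338: p = 0.007.
- Scaled to 237 vemurafenib patients: 237 × 0.02077 = 4.9; limits 237 × 0.00839 = 2.0 and 237 × 0.04233 = 10.0.
- Scaled to 237 placebo patients: 0, with upper limit 237 × 0.01085 = 2.6, or about 3.
- By cohort, vemurafenib arm: 150 × 7/337 = 3.1 in Cohort 1 and 87.5 × 7/337 = 1.8 in Cohort 2.

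These are patients whose SAE status for this event could turn on the section followed. The proportion of patients with any SAE changes only for those who have no other SAE.

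**The case against.** The strongest reply is that the protocol can be read as one rule. Section 5.1.2.3.5 does not forbid SAE reporting; it leaves melanoma out of its own instruction. Section 5.1.2.3.3 does not call new primary melanoma non-serious, although it does say so of cuSCC/KA one sentence earlier. Section 5.3 sends the seriousness assessment to 5.2.2, and 5.6 agrees with 5.2.2. A site that files every new primary melanoma as an SAE breaches none of these sections.

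This stands in part. A reader might infer that the sections cannot both be followed, or that 5.1.2.3.5 prohibits an SAE report. The text supports neither. But if 5.2.2 were meant to govern, the added words in 5.1.2.3.5 that exempt melanoma would have no purpose. They signal a different classification, and the section referred to does not supply it.

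A second reply is that little is lost. That is right for efficacy. New primary melanoma is a centrally confirmed DFS component, and all new primary malignancies are reported until the end of the study (5.3.1), so the cases are known however they are coded. Treatment-emergent events are also summarized by preferred term (6.5). What remains open is the seriousness flag, and with it the SAE totals.

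A reader might also infer that the distortion falls mainly on the vemurafenib arm. The 7/337 vs 0/338 makes that plausible but does not establish it here. That study was open-label, in metastatic disease, against dacarbazine, with median follow-up of 6.21 and 4.46 months (1.2.4). This trial is placebo-controlled, schedules the same skin examinations in both arms, and requires central pathology. Up to about 3 placebo cases are compatible with the same data. Nor do the documents show that any sites did diverge; the text only allows it.

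**Conclusion.** The protocol's current text classifies new primary melanoma inconsistently. Sections 5.2.2 and 5.6 count it among SAEs, 5.1.2.3.5 takes it out of the SAE instruction, and 5.1.2.3.3 and 5.2.3 give it no other category. Its SAE status, and whether the 24-hour duty applies, can depend on the section a site follows.

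The effect is modest: about 5 vemurafenib patients (range 2 to 10) and 0 to about 3 placebo patients, in safety tables only. This assumes that the earlier study's rates carry over and that every case turns on the section followed. The number is smaller if some cases are serious on a general criterion such as hospitalization or significant medical event. The primary and secondary efficacy analyses are untouched. The point is worth correcting because SAE incidence by arm is a stated outcome and the correction is cheap.

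**What to change.** 1. Reconcile Protocol 5.1.2.3.3, 5.1.2.3.5, 5.2.2, 5.2.3 and 5.6 to one reporting classification for new primary melanoma. Which one is for the sponsor to decide; the sections need to agree.
2. Check the seriousness coding of every centrally confirmed new primary melanoma already in the database against that classification, and query the mismatches. This has to come before tabulation, because a table row cannot recover a case that was never coded serious.
3. In the SAE summary under SAP 4.7.2, show new primary melanoma as its own line by arm, for each cohort and pooled, so that totals with and without it are visible.

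The cost is a few sentences in the protocol, a handful of data queries and one table row. Dosing ended on 14 September 2016 and the primary analysis is done, so the protocol wording now matters mainly for remaining follow-up. Steps 2 and 3 are what make the SAE totals in the final report interpretable.

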5.2.3 Non-Serious Adverse Events of Special Interest (Immediately Reportable to Roche)

Non-serious adverse event of special interest are required to be reported by the investigator to the Sponsor within 24 hours after learning of the event (see Section 5.4.2 for reporting instructions). Adverse events of special interest for this study include the following:

- Grade ≥ 3 photosensitivity
- Grade 4 elevations of AST, ALT, serum bilirubin OR cases of elevated ALT or AST in combination with either an elevated bilirubin or clinical jaundice, as defined in Section 5.3.5.6
- cuSCC (including KA)
- Grade ≥ 3 QT interval prolongation
- Gastrointestinal polyps
- Suspected transmission of an infectious agent by study drug

5.3 METHODS AND TIMING FOR CAPTURING AND ASSESSING SAFETY PARAMETERS

The investigator is responsible for ensuring that all adverse events as defined in Section 5.2.1 are recorded on the Adverse Event eCRF and reported to the Sponsor in accordance with instructions provided in this section and in Section 5.4 through Section 5.6.

For each adverse event recorded on the Adverse Event eCRF, the investigator will make an assessment of seriousness (see Section 5.2.2), severity (Section 5.3.3), and causality (Section 5.3.4).

5.3.1 Adverse Event Reporting Period

Investigators will seek information on adverse events at each patient contact. All adverse events, whether reported by the patient or noted by study personnel, will be recorded in the patient's medical record and on the Adverse Event eCRF.

After informed consent has been obtained **but prior to initiation of study drug**, only serious adverse events caused by a protocol-mandated intervention should be reported (e.g., serious adverse events related to invasive procedures such as biopsies).

After initiation of study drug, all adverse events, regardless of relationship to study drug, will be reported up to and including 28 days after the last dose of study drug. After

this period, investigators should report any deaths, serious adverse events, or other adverse events of concern that are believed to be related to prior treatment with study drug (see Section 5.6). In addition, all new primary malignancies will be reported *until end of study* (see Section 3.2), whether or not a patient has exhibited recurrence of melanoma while in the study.

